##### **4.4.1. Deviations Assessed Prior to Enrollment**

At screening, the investigator will assess subjects against the inclusion and exclusion criteria as set out in Sections 4.1 and 4.2 of the protocol.

##### **4.4.2. Deviations Assessed Post-Enrollment**

Deviations that might render a subject non-evaluable for the TIE assessment (excluding subjects who experienced any TIE), potentially necessitating a replacement for the respective cohort during the enrollment period and before the mCRM analysis is run to estimate the MTD include:

- Failure to administer the complete assigned dose of PF-05230907
- Dosing error of sufficient magnitude (underdose or overdose, per the Investigational Product Manual) such that observations from the respective subject would not be reflective of safety for the assigned dose level. Since our dose grid has doses spaced apart by about 25% (Table 2, column 2 from 5 µg/kg onward), actual dose exceeds or falls short of the assigned dose by at least 20% may be considered for a replacement for the respective cohort
- Withdrawal from the study prior to Day 8 (or discharge) for reasons other than study drug-related toxicity
- The informed consent was not signed
- Failure to meet inclusion/exclusion criteria when the resulting eligibility violation(s) adversely impacts the scientific or medical integrity of safety assessments in the respective subject. However, an enrollment or dosing outside of the 6 hours window

is not likely to compromise scientific/medical validity of safety assessments in the respective subject

- Failure to collect the protocol specified safety assessments during the interval from treatment through Day 8 (or discharge)
- Use of prohibited treatments (except when being used to treat an adverse event)

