3.1. Sequential Dosing

Sequential dosing of subjects will be implemented in each cohort evaluating a dose level that exceeds previously administered dose levels. An enrollment pause will be implemented following dosing of each subject in the cohort to allow for medical monitor safety data review prior to dosing the next subject. For the safety review that will take place during the enrollment pause, clinical observation results collected on the respective subject during the initial 72-hour period following dosing (treatment emergent adverse events [TEAEs], SAEs, vital sign changes, electrocardiogram [ECG] changes, Brain imaging study [CT ± MRI] scan, Doppler ultrasound of the lower extremity and cardiac troponin I [and cardiac troponin T, where applicable]) will be reviewed by the medical monitor. Other available laboratory test results at the time of this safety review will also be assessed.

If a Suspected Unexpected Serious Adverse Reaction (SUSAR) or 2 or more grade 3 or higher adverse events that are considered at least possibly related to treatment with PF-05230907 are observed in the initial cohort evaluating a dose level that exceeds previously investigated dose levels, then the subsequent (second) cohort evaluating the respective dose level will also be subject to sequential dosing restrictions.

Severity of adverse events (AEs) and serious adverse events (SAEs) will be graded according to the National Cancer Institute (NCI) Common Terminology Criteria for Adverse Events (CTCAE) version 4.03.¹⁰ TIEs will be defined as any of the listed events at the respective severity grade indicated in [Appendix 1](#). All subjects who receive PF-05230907 are evaluable for TIEs. The determination of MTD using mCRM dose-toxicity modeling will be based on TIEs which occur through 7 days post-dose (Day 8).

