3.2. Progression to Subsequent Cohort

A target 15% TIE rate at the MTD will be employed for the MTD determination. The range of doses that may be explored will be from a grid of doses ranging from 1 $\mu\text{g}/\text{kg}$ to 47 $\mu\text{g}/\text{kg}$ ([Table 2](#)). Subjects will be enrolled in cohorts, starting with an initial dose of 5 $\mu\text{g}/\text{kg}$ for the first cohort (the highest dose safely administered in the first in human clinical study [B2341001]). If the modeled rate of TIEs at the 5 $\mu\text{g}/\text{kg}$ starting dose exceeds the pre-specified target toxicity rate of 15% for the MTD, lower doses may be explored. Starting with the second cohort, subjects will be assigned to a dose in the pre-defined dose grid that is closest to, but not exceeding, the currently predicted MTD based on a parametric dose-toxicity model that the mCRM utilizes to learn about the overall dose-TIE relationship subject to additional dose escalation constraints and clinical oversight. The dose-toxicity model is updated based on the frequency of TIEs in each completed cohort. Under the adopted mCRM design, the dose level for each subsequent cohort can be escalated, deescalated, or restudied but always aiming towards the MTD target based on the frequency of TIEs. However, dose level assignments may be modified to more conservative dose levels based upon sponsor medical judgment or eDMC recommendations. To prevent overly aggressive dose-escalation, the maximum allowed dose increase from the highest dose that has been previously studied is limited to 2 increments at a time (ie, not more than one dose level may be skipped-see ([Table 2](#)), which results in 50-67% increase in dose from the 5 $\mu\text{g}/\text{kg}$ dose and above. If treatment emergent modulation of one or more of the following laboratory safety biomarkers is observed during the interval from baseline to Day 4 (where available), as indicated below, dose increase will be limited to only 1 increment at a time (ie, no more dose skipping):

- Fibrinogen:
 - If baseline value is within normal reference range: a post-dose value $\leq 50\%$ of the lower limit of normal.
 - If baseline value $<$ lower limit of normal reference range: a post-dose value $\leq 50\%$ of the baseline value.
- Platelet Count:
 - If baseline value is within normal reference range: a post-dose value of $< 100,000$.

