3.4. Stopping Rules for mCRM Algorithm

Study enrollment will stop if (1) the maximum sample size has been achieved (51 subjects), (2) 12 subjects have been accumulated on a dose that is predicted to be the MTD by the fitted dose-toxicity curve or (3) all doses appear to be overly toxic and the MTD cannot be determined in the current trial. Available doses and percentage increments between doses corresponding to possible dose-escalation steps (1, or 2 at a time) are summarized in the table below ([Table 2](#)). Note that a particular dose-assignment sequence and number of subjects treated at each dose cannot be pre-specified in advance due to the dynamic nature of the Bayesian allocation procedure, and not every dose listed will be actually studied. Doses will be limited to the maximum that has been specified in [Section 1.5](#).

Subjects who withdraw prior to Day 8/discharge may be replaced at the discretion of the Sponsor. Additional subjects may be added to one or more cohorts to further define the MTD or safety of PF-05230907.

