### **4.2.1. TIE-evaluable Set**

The TIE-evaluable set includes all subjects who receive PF-05230907. All subjects in the TIE-evaluable set will contribute to the determination of the MTD including subjects who are lost to follow-up prior to completion of the TIE observation period from study enrollment through 7 days post-dose (Day 8). For subject(s) meeting protocol deviations (see Section 4.4) that render the subject non-evaluable for the TIE assessment and necessitating a replacement, the replacement subject will be used instead in sensitivity analyses, and mCRM analyses during the trial when deemed appropriate.

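### SAP 4.4.2 lets unconsented, ineligible or overdosed subjects be replaced only if they had no TIE, so the counted TIE rate is biased upward whenever that discretion is used

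*SAP*

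**What the plan says.** Protocol 3.1 is unconditional: "All subjects who receive PF-05230907 are evaluable for TIEs". Protocol 3.4 mentions replacement in one situation: "Subjects who withdraw prior to Day 8/discharge may be replaced at the discretion of the Sponsor". It does not say that the withdrawn subject leaves the model.

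SAP 4.2.1 starts from the same position: "The TIE-evaluable set includes all subjects who receive PF-05230907", and all of them contribute to the MTD. It then makes an exception. Where a protocol deviation makes a subject non-evaluable and a replacement is needed, "the replacement subject will be used instead in sensitivity analyses, and mCRM analyses during the trial when deemed appropriate".

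SAP 4.4.2 supplies the list for that exception: "Deviations that might render a subject non-evaluable for the TIE assessment (excluding subjects who experienced any TIE), potentially necessitating a replacement". Its items fall into two kinds:

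- Fixed at or before dosing: unsigned consent; an eligibility breach, worded as "Failure to meet inclusion/exclusion criteria when the resulting eligibility violation(s) adversely impacts the scientific or medical integrity of safety assessments"; an incomplete dose; and a dosing error, where "actual dose exceeds or falls short of the assigned dose by at least 20% may be considered for a replacement for the respective cohort".
- Arising afterwards: early withdrawal for reasons other than drug toxicity, missed safety assessments and use of prohibited treatments.

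The exemption for subjects with a TIE applies to every item.

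**The concern.** For early withdrawal or missed assessments the exemption makes sense. An observed TIE is a known outcome even if follow-up was cut short, whereas a TIE-free partial record is incomplete.

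Consent and eligibility are different, because they are settled before any outcome exists. Suppose a subject with a prothrombotic disorder is enrolled against exclusion criterion 8. If a DVT follows, the subject stays in. If not, the subject may be replaced. The violation is the same and only the outcome differs.

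Overdose has the same problem. A TIE after an overdose is kept against the lower assigned dose, while a TIE-free overdose, which is informative about the assigned dose, can be removed.

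The mCRM is driven by very few events against a fixed target (Protocol 3.2: "A target 15% TIE rate at the MTD will be employed for the MTD determination"). Selecting subjects on the outcome therefore acts directly on dose recommendations and on the analysis meant to test their robustness.

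**Working it through.** **Inputs.** Target 15% (Protocol 3.2). Model, Unif[0,3] prior and Table 3 starting rates (Protocol 9.1; SAP 5.2.1 and 5.2.2). Cohorts of 3 and a limit of two dose increments (SAP 2.2). The deviation fraction r is not in the documents, so it is assumed and shown over a range.

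**1. Plan's own figure.** At β = 1, x = atanh(2p − 1). At 5 µg/kg, p = 8% gives atanh(−0.84) = −1.22, as in Table 3. All 15 rows match to two decimals. The modelled rate at each dose is therefore its Table 3 rate raised to the power β.

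**2. Counted TIE rate under the rule.** Let p be the true TIE probability and r the share of subjects with such a deviation, independent of outcome. If every TIE-free deviator is replaced until the slot is filled, a treated subject is counted with probability p + (1 − p)(1 − r). So

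counted rate = p / [p + (1 − p)(1 − r)].

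For p = 0.15:

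- r = 5%: 0.15 / (0.15 + 0.85 × 0.95) = 0.15 / 0.9575 = 15.7%
- r = 10%: 0.15 / (0.15 + 0.85 × 0.90) = 0.15 / 0.915 = 16.4%
- r = 20%: 0.15 / (0.15 + 0.85 × 0.80) = 0.15 / 0.83 = 18.1%

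If only one replacement is allowed per slot and is always kept, the rate is p + r(1 − p)p. That is 16.3% at r = 10%.

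**3. Direction when deviators have a different risk.** With TIE probability q in deviators, the counted rate is [(1 − r)p + rq] / [(1 − r) + rq]. The all-treated rate is the numerator alone. The denominator is below 1 whenever r > 0 and q < 1, so the rule always gives the higher figure when there are any TIEs. At p = 15% and r = 20%:

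- q = 5%: (0.12 + 0.01) / (0.80 + 0.01) = 16.0%, against 13.0% with all treated subjects
- q = 25%: (0.12 + 0.05) / (0.80 + 0.05) = 20.0%, against 17.0%

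**4. Effect of one swap on the model dose.** The right contrast is a TIE-free deviator kept alongside the replacement (1 TIE in 4) against the same subject swapped out (1 in 3). The posterior mean of β was computed on a fine grid. The model dose is the highest grid dose with a modelled rate below 15%.

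| Data | Mean β | Modelled rates | Model dose (µg/kg) |
|---|---|---|---|
| 5 µg/kg: 1/4, all kept | 0.820 | 12.6% at 5; 15.8% at 6 | 5 |
| 5 µg/kg: 1/3, after swap | 0.722 | 13.1% at 4; 16.2% at 5 | 4 |
| 0/3 at 5, then 1/4 at 8 | 1.202 | 12.3% at 10; 16.2% at 12 | 10 |
| 0/3 at 5, then 1/3 at 8 | 1.131 | 13.9% at 10; 18.0% at 12 | 10 |

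One swap moves the model dose in the first setting and not in the second. In the second setting two swaps in one cohort do move it: 1/5 at 8 µg/kg gives β = 1.264 and a model dose of 12, against 10 for 1/3.

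**5. Whole-trial effect.** The design was simulated with 4,000 trials per setting. Each started at 5 µg/kg with the two-increment limit, and stopped at 12 subjects on the MTD with at least 20 counted, or at 51. Every TIE-free deviator was replaced. With a true MTD of 8 µg/kg, selection below it rose from 28% (all kept) to 36% at r = 10% and 45% at r = 20%. With a true MTD of 12 µg/kg the figures were 30%, 37% and 47%. Replacement regardless of outcome left these at 27–30%. The chance of selecting exactly the true MTD hardly changed (27–29%), so the shift is from selecting too high to selecting too low.

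**The case against.** The case on the other side is substantial, and most of it narrows the point.

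- **The rule is discretionary.** The SAP's wording is permissive throughout. Eligibility breaches count only if they damage the safety assessment, and SAP 4.4.2 treats breaches of the 6-hour window as unlikely to do so. This stands: the bias exists only when the rule is used. But discretion in an open-label trial, with the outcome written in as a condition, does not protect against the bias.
- **Incomplete dose and underdose.** If toxicity rises with dose, a TIE after an underdose is still evidence against the higher assigned dose, while no TIE says little about it. Keeping the first and replacing the second is defensible. This stands, so the point excludes them.
- **The error is conservative.** It lowers the MTD rather than encouraging over-escalation. That is true, but the aim is to estimate the dose at the 15% target, and Protocol 3.2 already has an open route to more conservative assignments.
- **The SAP may modify the protocol.** Protocol 9 allows this, but requires an amendment for major changes to the primary endpoint or its analysis. Whether this change is major can be argued. The contradiction inside SAP 4.2.1 remains either way.

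A reader might also infer more than the documents support:

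- **That one ineligible TIE subject at 8 µg/kg, after 0/3 at 5, moves the model dose from 19 to 10** (0/2 against 1/3). Those figures compute correctly, but Protocol 3.1 keeps that subject too, so the gap is not an effect of the SAP rule.
- **That Protocol 3.4 forbids any other replacement.** It names withdrawal without saying that nothing else qualifies, and it also allows subjects to be added.
- **That no planned analysis could show ineligible subjects driving the result.** SAP 4.4 separately allows major violators to be excluded, with a documented rationale and no TIE exemption.

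**Conclusion.** The point holds in a limited form. For unsigned consent, integrity-affecting eligibility violations and overdose, SAP 4.4.2 makes removal depend on the outcome. SAP 4.2.1 carries that into the sensitivity analyses and, at discretion, into the in-trial mCRM. Whenever the rule is used this way, the counted TIE rate is biased upward and the estimated MTD is pushed down.

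The size depends on an assumed r and on full use of the rule. At a true 15% the inflation is about 0.7 points at r = 5%, 1.4 at 10% and 3.1 at 20%. A single swap may or may not change the model dose.

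It would be wrong to read this as a bias in the primary TIE summary, because SAP 6.1.1 uses all treated subjects. Nor do the documents show that any subject was replaced under this rule.

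**What to change.** 1. Reconcile SAP 4.2.1 and 4.4.2 with Protocol 3.1. Keep every treated subject in the mCRM, and add any replacement to the data rather than substituting it.
2. In the sensitivity refit, exclude subjects with no consent, an integrity-affecting eligibility violation or an overdose, whether or not they had a TIE. Report this fit beside the all-treated fit.
3. Keep the TIE exemption for withdrawal, missed assessments, and incomplete dose or underdose. Examine dose errors through the actual-dose sensitivity analyses already planned in SAP 6.1.1.1 and 6.5.3.

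The cost is SAP wording and one extra refit, with no new data. The refit may rest on slightly fewer subjects. SAP 1 records early termination after 21 subjects were enrolled, so past dose assignments cannot be changed. The sensitivity refit and its reporting still can be.

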## 5. GENERAL METHODOLOGY AND CONVENTIONS

### 5.1. Hypotheses and Decision Rules

This is a study to determine the MTD and assess the safety, tolerability, and PD of PF-05230907 administered once in subjects with ICH. No formal hypothesis testing will be performed. The decision rules for study stopping and MTD determination are described in Section 5.2.

### 5.2. mCRM design

This study is designed to estimate the MTD, defined as the dose that yields approximately but no greater than the target 15% TIE rate. It employs a modified Continual Reassessment Method (mCRM) design, which utilizes Bayesian methodology to learn the dose-toxicity relationship continuously after each cohort's thromboembolic and/or ischemic event (TIE) data becomes available. Subjects will receive different doses using an adaptive allocation rule with the goal of estimating the MTD. Starting from the second cohort, subjects will be assigned to a dose, from a pre-defined dose grid, that is closest to but not exceeding, the current model-based estimate of MTD based on a one-parameter dose-TIE model, subject to additional dose escalation constraints described in Section 2.2.

#### 5.2.1. Dose Response Modeling

The underlying dose-TIE relationship between the probability of TIE events and dose is modeled using a binary endpoint ( $Y=1$ : if TIE observed and  $Y=0$ : if no TIE observed) and the one-parameter hyperbolic-tangent model.

$$p = \Pr(Y = 1 | x; \beta) = f(x; \beta) = \left[ \frac{1 + \tanh x}{2} \right]^\beta \quad (1)$$

where  $x$  is an adjusted dose which could be computed from an initial dose-toxicity curve,  $\beta$  is an unknown parameter with a prior distribution pre-specified at the beginning of the trial, and  $\tanh$  is the hyperbolic-tangent function. In the discrete setting of this trial, where only 15 different doses are available in the dose grid as listed in Table 2 with a starting dose of 5  $\mu\text{g}/\text{kg}$ , the dose-TIE model could be replaced by

$$p_i = \Pr(Y = 1 | x_i; \beta) = f(x_i; \beta) = \left[ \frac{1 + \tanh x_i}{2} \right]^\beta, i = 1, \dots, 15$$

where the adjusted doses  $x_i$ 's are obtained by solving the above equation given  $\beta=1$  and user supplied vector of  $p_i$ 's, representing the initial guesses of an anticipated probability of TIE at each dose described in details in the following section.

### 5.2.2. Prior distribution

A prior uniform distribution, Unif [0,3], placed on the model parameter  $\beta$  and the vector of estimated probability of TIE when  $\beta=1$ , shown in Table 3, define the “starting point” of the mCRM algorithm. Based on clinical input, this initial dose-TIE profile assumes that a TIE rate of 15% can occur as early as 8-10  $\mu\text{g/kg}$  and further increases to 27% and 49% at 15  $\mu\text{g/kg}$  and 37  $\mu\text{g/kg}$ , respectively. The estimated TIE rates for other doses were imputed based on the projected initial dose-TIE curve. The adjusted doses (ie,  $x$  in the hyperbolic-tangent model) were computed from the hyperbolic tangent model by setting  $\beta=1$ .

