1.4. Study Rationale

This study will determine the maximum tolerated dose (MTD) of PF-05230907 and evaluate safety and tolerability of a single administration of PF-05230907 in subjects with spontaneous intracerebral hemorrhage (ICH). Given the severe morbidity and mortality associated with the condition and given the need to better define the maximum tolerated dose of PF-05230907 in order to plan future efficacy studies, a modified continual reassessment method (mCRM) will be implemented to determine the MTD (see [Section 9](#)) based on frequency of treatment emergent thromboembolic and/or ischemic events (to be referred to as TIEs throughout this document). A target TIE rate of 15% represents approximately a 5-10% increment above the background rate and is considered compatible with acceptable benefit risk in the high morbidity, high mortality indication of ICH. A background rate of approximately 5-10% in the ICH population is based upon published literature for spontaneous ICH from studies of activated coagulation factor VII in ICH and the placebo-treated subject-level datasets from 4 studies performed contemporaneously with the clinical studies of NovoSeven in ICH contained within the Virtual International Stroke Trial Archive (VISTA).^{7,8,9} The TIE rate in the internal analysis of the VISTA placebo datasets filtered to reflect the intended population for treatment with PF-05230907, was approximately 5.5% within the first 8 days from the baseline computed tomography (CT) scan.

Selection of the PD biomarkers included in the study (aPTT and PF1+2) is informed by the results from the study B2341001. The PD results will provide information on target engagement and coagulation pathway activation at the various dose levels studied.

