##### **3.1.1. Treatment emergent TIEs through Day 8**

Thromboembolic and/or ischemic events (TIEs) are defined as any of the listed events at the respective severity grade indicated in Appendix 1. The first primary endpoint is defined as

the frequency of treatment emergent TIEs in subjects treated with PF-05230907 through Day 8. For the respective event to count as a treatment emergent TIE, onset or worsening of the event must occur following treatment with PF-05230907 and during the interval between Day 1 dosing through Day 8.

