### 6.1. Primary Endpoints

#### 6.1.1. Treatment emergent TIEs through Day 8

The primary analyses will be based on the TIE-evaluable set. Treatment emergent TIEs will be listed and summarized overall and by dose group. The summary Tables include:

- Treatment emergent TIEs (all causalities) by system organ class and preferred term
- Treatment emergent TIEs (treatment related) by system organ class and preferred term
- Incidence and severity of treatment emergent TIEs (all causalities, treatment related)

As discussed in Section 5.2, the TIE data from the current cohort (and previous cohort[s]) will be utilized for the mCRM dose-toxicity modeling along with clinical and eDMC oversight to determine the MTD. The following Figures will be generated:

- Vertical bar chart of the number of treatment emergent TIEs by dose group used in the mCRM dose-toxicity modeling
- Estimated Dose-TIE toxicity response curve with 95% confidence interval around the fitted curve, superimposed on the number of subjects allocated to each dose group in a vertical bar chart format, and the observed proportion of treatment emergent TIE at each dose level
- Allocation of subjects at each dose and corresponding TIE toxicity response (red dot denotes treatment emergent TIE) showing how dose-escalation scheme progresses over time via the order of study enrollment and observed number of treatment emergent TIEs

For the interim analysis of the treatment emergent TIEs, refer to Section 7 for details.

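### The dose-TIE model has no background term, so the fitted curve and its planned 95% band are likely to run too low at doses well below the MTD

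*SAP*

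**What the plan says.** - **Model.** SAP 5.2.1 relates dose to the probability of a TIE with a "one-parameter hyperbolic-tangent model", f = [(1 + tanh x)/2]^beta. There is no intercept or floor. SAP 5.2.2 gives beta a Unif[0,3] prior and takes the rates at beta = 1 from Table 3: 2.5%, 3.3%, 4.5%, 6% and 8% at 1 to 5 µg/kg, rising to 55% at 47 µg/kg. A few points rest on clinical input. For the rest, "The estimated TIE rates for other doses were imputed based on the projected initial dose-TIE curve".
- **Endpoint.** SAP 3.1.1: "For the respective event to count as a treatment emergent TIE, onset or worsening of the event must occur following treatment with PF-05230907". Causality is not part of the definition.
- **Background.** Protocol 1.4: "A background rate of approximately 5-10% in the ICH population is based upon published literature for spontaneous ICH". In the filtered placebo data the rate "was approximately 5.5% within the first 8 days from the baseline computed tomography (CT) scan". The same section says "A target TIE rate of 15% represents approximately a 5-10% increment above the background rate", so 15% is a total rate that includes background.
- **Output.** SAP 6.1.1 lists among its TIE figures "Estimated Dose-TIE toxicity response curve with 95% confidence interval around the fitted curve", with the observed proportions and numbers treated overlaid. It does not say how the interval is constructed.
- **Robustness.** The sensitivity analyses in SAP 6.1.1.1 and 6.5.3 concern weight-based and actual dose, not the form of the curve.

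No section reconciles the fitted low-dose rates with the background.

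**The concern.** If untreated patients have a TIE rate of 5-10% and every post-dose TIE counts, the total rate at a very low dose should settle near that level. The fitted curve instead heads to zero as dose falls, and it does so faster as beta rises. Because one parameter sets the whole curve, a low event rate at high doses forces near-zero rates at low doses, with a narrow band around them.

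A reader of the published figure could then see well under 1% at the starting dose, in a population whose own background is 5-10%, and take it as a finding of negligible risk. Nor could the low-dose part of the curve be compared with the increment over background that Protocol 1.4 uses to justify the 15% target.

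**Working it through.** **1. Reproduce Table 3.** At beta = 1, x = ½ ln[p/(1−p)]. For 8%, ½ ln(0.08/0.92) = −1.22, as printed. All 15 values agree to two decimals. A rate of 15% falls between 8 µg/kg (13.5%) and 10 µg/kg (17.5%), as SAP 5.2.2 states.

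**2. When the curve drops below background.** The fitted rate at a dose is (Table 3 rate)^beta. At 5 µg/kg it is below 5.5% once beta > ln 0.055 / ln 0.08 = 1.148, and below 5% once beta > ln 0.05 / ln 0.08 = 1.186. At the prior mean of 1.5 it is 0.08^1.5 = 2.26%. At 8 µg/kg it is 0.135^1.5 = 4.96%, so every dose from 1 to 8 µg/kg is below 5%.

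**3. What a given MTD forces at 5 µg/kg.** If the fitted rate is exactly 15% at a dose with Table 3 rate r, then beta = ln 0.15 / ln r and the rate at 5 µg/kg is 0.08^beta.

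| Estimated MTD (µg/kg) | r | beta | Fitted rate at 5 µg/kg |
|---|---|---|---|
| 12 | 22% | 1.253 | 4.2% |
| 15 | 27% | 1.449 | 2.6% |
| 19 | 32.5% | 1.688 | 1.4% |
| 24 | 38% | 1.961 | 0.7% |

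**4. Coverage of the band.** The simulations follow the plan's dosing rules: cohorts of 3, start at 5 µg/kg, dose at or below the estimated MTD, at most two levels above the highest dose studied. They stop at 21 subjects, the number enrolled according to SAP 1. Assumed truth: 0.055 + 0.945 × (Table 3 rate)^beta. Assumed band: the Table 3 rate raised to the 97.5% and 2.5% posterior quantiles of beta.

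| True beta | True MTD | True rate at 5 µg/kg | Coverage at 5 µg/kg |
|---|---|---|---|
| 1.5 | 10 | 7.6% | 83% |
| 2.0 | 15 | 6.1% | 71% |
| 2.5 | 24 | 5.7% | 58% |

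- At 1 µg/kg, coverage runs from 54% down to 22% over the same rows. At the true MTD it is about 88%.
- The upper limit at 5 µg/kg lies below 5.5% in roughly 10%, 25% and 40% of trials.
- With a 10% background (0.10 + 0.90 × the same terms, true MTD 8, 12 and 15), coverage at 5 µg/kg is 75%, 62% and 57%.
- Runs of 600 to 3,000 trials per scenario agreed within about four points.

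**5. Is the missing floor the cause?** With the 51-subject cap and a truth inside the model family (no background), coverage is 94-98%. With a 5.5% floor and true MTDs of 8 to 24 µg/kg, it falls from 84% to 43% at 5 µg/kg. More data do not help: for one true curve with MTD 10, coverage at 5 µg/kg is 85% with 21 subjects and 80% with the 51 cap, because the band narrows around the wrong value. When the true MTD is 4 or 5 µg/kg the loss is small (91% and 88%).

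**6. Example (assumed counts; the trial's own are not in the documents).** Take 0/3, 0/3, 0/3, 1/6 and 1/6 at 5, 8, 12, 19 and 24 µg/kg. The posterior mean of beta is about 2.0, the MTD is 24, and the fitted rate at 5 µg/kg is 0.6% with a band of about 0.06% to 6%. The exact binomial interval for 0/3 has upper limit 1 − 0.025^(1/3) = 71%, which is what three subjects actually show.

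**The case against.** The strongest reply is that this is a working model whose job is to locate the dose with a 15% total rate, and near that dose the band does reasonably well. The figure also shows the observed proportions, so misfit at studied doses would be visible. Doses of 1-4 µg/kg come into play only if the modelled rate at 5 µg/kg exceeds 15%, that is, if beta < ln 0.15 / ln 0.08 = 0.751. At that value the rates at 1, 2 and 3 µg/kg are 6.3%, 7.7% and 9.7%, inside the background range. The trial stopped at 21 subjects, and the SAP cut analyses for that reason. All of this stands, and it confines the point to reporting. It does not make the low-dose interval a valid 95% interval. SAP 5.2.2's remark that data overrule the prior does not help either, since the fault is in the shape of the curve.

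A reader might infer more than the documents support:

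- **That background events pull the MTD down.** The target is a total rate, so background belongs in it. In the 5.5%-background simulations the mean error was +0.9, 0.0 and −1.1 grid levels at true MTDs of 10, 15 and 24: no consistent direction.
- **That the plan would declare a low MTD for an inert drug because the floor is missing.** At 10% background, an MTD of 15 µg/kg or less was declared in about 45% of trials with or without a floor. That reflects small numbers near a 15% target.
- **That the model form forces Table 3 below background.** Table 3 is a user-supplied vector and could have been set higher. Its 8% at 5 µg/kg is inside 5-10%. The trouble comes when beta exceeds 1.
- **That the curve is the trial's primary figure.** SAP 6.1.1 lists three figures and ranks none.

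**Conclusion.** The point holds for the reported low-dose curve and its interval. By the plan's own figures, any fit with beta above about 1.15 puts the starting dose below the 5.5% background. The nominal 95% band then covers about 58-83% at 5 µg/kg and 22-54% at 1 µg/kg in 21-subject trials with a true MTD of 10-24 µg/kg. The shortfall is mild if the MTD is near 5 µg/kg and severe if it is well above. Not every data set gives a band that excludes the background.

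This rests on three assumptions: an equal-tailed posterior interval, since the SAP gives no construction; a smooth true curve that levels off at Protocol 1.4's background; and simulated rather than actual TIE counts. Nothing here shows that the MTD estimate or the in-trial dosing is wrong.

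**What to change.** In SAP 6.1.1:

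1. State how the 95% interval around the curve is built.
2. Put exact binomial 95% intervals on the observed TIE proportion at each studied dose.
3. Draw Protocol 1.4's 5-10% background as a reference band on the figure.
4. Do not report model-based rates or bands below background as estimates, and name the cut-off. The 5.5% figure is the one tied to an 8-day window.
5. State that the working-model curve is interpretable only near the estimated MTD.

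Leave the in-trial dosing model unchanged.

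A refit with a background floor p0 in SAP 6.1.1.1 is optional and exploratory, and only with the skeleton and prior fully specified. Subtracting p0 = 10% from Table 3 gives negative values for 1-5 µg/kg (8% − 10% = −2% at the starting dose), so the recipe is undefined there. In simulation a floor refit still covered only 66-79% at 5 µg/kg when the true background was 10%, and it overshot the MTD more often than the planned model at true MTDs of 8-15 µg/kg. On sparse data its low-dose band largely restates the assumed floor.

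The cost is SAP wording and a revised figure. The low-dose intervals become wide: zero events in 3 subjects gives an upper limit of 71%, and zero in 12 gives 1 − 0.025^(1/12) = 26%. The figure will look less favourable.
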